1.4.1 Primary Endpoint 1 Results

The purpose of primary endpoint 1 is to evaluate the Sentus QP related complication-free rate through 6 months post-implant. Reported adverse events that were related to the implanted CRT-D system and/or implant procedure were adjudicated by the CEC. Events that occurred prior to or on the date of the 6 month follow-up and were adjudicated by the CEC as meeting the primary endpoint criteria were included in the calculation of the primary endpoint 1 complication-free rate. For the purposes of the primary endpoint 1 analysis, evaluable subjects are those who were included in the pre-market cohort and either completed a 6 month follow-up visit (n = 274), experienced an endpoint related adverse event but exited the study prior to reaching the 6 month follow-up

(n = 2), did not complete a 6 month follow-up visit but did complete a subsequent visit (n = 3), or had an unsuccessful implant due to a Sentus QP lead related complication (n = 0). Subjects in the pre-market cohort that did not have a successful Sentus QP implant were not included in the endpoint 1 analysis (unless, as noted above, the unsuccessful implant was due to a Sentus QP lead related complication). The total number of evaluable subjects for primary endpoint 1 was 279.

Analysis

Primary endpoint 1 was evaluated by performing an exact, binomial test comparing the observed proportion (complication-free rate at 6 months) to 90.0%.

Of the 279 evaluable subjects for primary endpoint 1, eight subjects had an event that met the primary endpoint criteria, were adjudicated by the CEC as related to the Sentus QP lead, and occurred prior to or on the date of the 6 month follow-up. The complication-free rate through 6 months post-implant is 97.1% (271/279), 95% CI of 94.4% to 98.8%, $p < 0.0001$.

Table 2 provides a summary of the eight primary endpoint 1 adverse events.

Table 2: Primary Endpoint 1 Adverse Event Summary

Adverse Event Type	Subjects with AE	% with AE	Number of AEs	Rate (per subject year)
Lead dislodgement	4	1.43%	4	0.028
Extracardiac stimulation	3	1.08%	3	0.021
Lead impedance out of range, high	1	0.36%	1	0.007
Total	8	2.87%	8	0.055

Total number of implanted subjects = 279; Subject years since successful implant = 144.7

Conclusion

The results indicate that the complication-free rate through 6 months post-implant is greater than 90.0%; therefore, primary endpoint 1 is met.

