2.3.2 Primary Endpoint 1 Analysis

The analysis population for primary endpoint 1 will include all subjects who provided informed consent, met the enrollment criteria, and in whom a Sentus QP lead was successfully implanted. The common scenarios listed below will be taken into account for analysis of primary endpoint 1:

- Subjects who completed a 6 month follow-up or experienced an adverse event (as defined in Section 6.6.1) prior to reaching the 6 month follow-up time point will be included in the endpoint evaluation.
- Subjects without an adverse event (as defined in Section 6.6.1) who exit the study prior to the 6-month follow-up are excluded from the analysis population to avoid an overestimation of the complication-free rate.
- Subjects that were not successfully implanted due to a Sentus QP lead related complication (such as coronary sinus dissection caused by the Sentus QP lead) will be included in the population.
- Any subject with a missing 6 month follow-up, who completes a subsequent follow-up (e.g. 12 month follow-up or interim follow-up) will be included in the evaluation.

Primary endpoint 1 will be evaluated by performing an exact, binomial test comparing the observed proportion (overall complication-free rate at 6 months) to the performance goal of 90.0%. The lower, two-sided 95% confidence bound for the overall complication-free rate must be greater than 90.0%.

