2.3.4 Primary Endpoint 3 Analysis

The analysis population for primary endpoint 3 will include all subjects who provided informed consent, met the enrollment criteria, and in whom a Sentus QP lead was successfully implanted. Only subjects who were successfully implanted and completed a 60-month month visit will be included in the endpoint analysis

Primary endpoint 3 will be evaluated by performing an exact, binomial test comparing the observed proportion (overall complication-free rate at 5 years) to the performance goal of 92.5%. The lower, two-sided 95% confidence bound for the overall complication-free rate must be greater than 92.5%.

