2.3.5 Secondary Endpoints

The secondary endpoints of pacing threshold (programmed and novel pacing vectors), sensed amplitude, and impedance at the 3 month visit will be summarized using standard measures, including means, standard deviations, medians, minimum and maximums. In addition, the percentage of subjects with values within the acceptable range per lead model will be provided. Acceptable ranges for the lead measurements are provided in Section 3.2.5.

For secondary endpoints 1-4 only subjects who were successfully implanted, completed a 3 month visit, and have data for the specific endpoint being evaluated will be included in the endpoint analysis; however, additional data resources may be used for supplemental analysis.

For the endpoint 5, time-to-first-complication, the analysis set of the primary endpoint 1 and additionally also those subjects who drop out prior to the 6-month follow-up is used. Confidence intervals based on Kaplan-Meier estimates for freedom from complications together with the associated standard errors will be provided. For this estimate, subjects exiting the clinical investigation prior to the 6 month visit will be censored at the time of study termination.

For endpoint 7 and 8, only subjects who were successfully implanted and completed a 60-month month visit will be included in the endpoint analysis; however, additional data resources may be used for supplemental analysis.

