2.3.7 Trend Analyses

The primary post-approval safety endpoint is evaluated at 5 years post-implant against a prespecified performance level (92.5% for overall freedom from Sentus QP related complications). To monitor the ongoing incidence of any potential AEs against the accumulating follow-up exposure post-implant, a Kaplan-Meier survival curve will be prepared at the reporting intervals for this safety outcome. Root causes for any failures, regardless of the incidence rates, will be investigated.

If the observed cumulative survival rate falls below the 5-year target value (92.5% of overall freedom from complications) at any time during the study, or is projected to fall below the target value, then BIOTRONIK will summarize the observed data and the results of the failure investigations, and report the findings to the FDA at or before the next scheduled reporting interval. If at any time a single unanticipated adverse event or device failure, or combination of events, is believed to have implications regarding the safety of current or future subjects, then this will be reported to the FDA within the statutory timeframes.

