3.5.2.2 Unsuccessful implant

If a Sentus QP lead came in contact with the subject but could not be implanted, an adverse event or device complaint should be completed and the subject exited. Data for subjects that have a Sentus related adverse event according to the listing provided in Section 6 will be included in analysis.

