3.5.2.5 Sentus QP lead extraction

Any subject who has the Sentus QP lead explanted and not replaced with another Sentus QP lead will be withdrawn from the clinical investigation. After documentation of the system revision procedure (see Section 3.4.7.2), a Study Termination eCRF should be completed.

Whenever possible, devices that are explanted must be returned to BIOTRONIK, Inc. for analysis.

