- Pneumothorax directly associated with the Sentus QP lead
- Cardiac perforation with or without tamponade caused by the Sentus QP lead
- Coronary sinus dissections directly caused by the Sentus QP lead (e.g., dissections caused by lead delivery device are excluded)

Finally, subject deaths resulting from a Sentus QP lead-related AE will be included in the primary endpoint analysis.

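### The 5-year primary safety test counts only subjects who reach a 60-month visit, so complications that end participation drop out of the analysis and the complication-free rate is biased upward

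*Combined protocol and SAP*

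**What the plan says.** Section 2.3.4 opens by defining the endpoint 3 population as consented, eligible subjects with a successful Sentus QP implant. It then narrows this: "Only subjects who were successfully implanted and completed a 60-month month visit will be included in the endpoint analysis". The test is an exact binomial comparison with 92.5%. Section 2.3.5 applies the same restriction to the per-model rates and the individual event rates: "For endpoint 7 and 8, only subjects who were successfully implanted and completed a 60-month month visit will be included in the endpoint analysis". It adds that other data may be used for supplemental analysis.

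Other sections define failures and exits:

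- Table 8 (Section 6.6.2) counts qualifying events resolved by surgical explant or abandonment, up to the 60-month visit.
- Section 6.6.2 also says that "subject deaths resulting from a Sentus QP lead-related AE will be included in the primary endpoint analysis".
- Section 3.5.2.5: "Any subject who has the Sentus QP lead explanted and not replaced with another Sentus QP lead will be withdrawn from the clinical investigation". Section 3.5.3 sets the termination date at the explant or the death.
- Section 3.5.2.2, on unsuccessful implants where the lead touched the subject: "Data for subjects that have a Sentus related adverse event according to the listing provided in Section 6 will be included in analysis".

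Endpoint 1 was handled differently. Section 2.3.2 keeps this group in the evaluation: "Subjects who completed a 6 month follow-up or experienced an adverse event (as defined in Section 6.6.1) prior to reaching the 6 month follow-up". Implant failures caused by the lead are counted there as well.

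Section 2.3.7 says that "a Kaplan-Meier survival curve will be prepared at the reporting intervals for this safety outcome", and Section 2.5.4 censors early exits at study termination. That curve is for trend monitoring and is not the endpoint 3 test.

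**The concern.** A completers-only proportion is roughly unbiased if leaving the study has nothing to do with having a complication. Here the protocol itself links the two: an explant without a new Sentus QP lead is a failure that forces withdrawal, and a lead-related death is a failure that rules out the visit. Section 2.4.2 lists mortality and device explant among the exits that make up the 11% yearly attrition.

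The estimate then describes subjects who, with a Sentus QP lead, stayed in the study for 5 years. Exits caused by complications can only push it upward. At stake is the error rate of the only primary hypothesis of the 5-year study. Secondary endpoint 8, which should describe each event type, would lose the events serious enough to end participation. The Kaplan-Meier curve of Section 2.3.7 would count those events, so two planned analyses of one outcome could disagree.

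**Working it through.** **Inputs.** Section 2.4.2: p0 = 0.925, p1 = 0.9475, one-sided alpha 2.5%, power 80%, 979 evaluable, attrition 11% per year, 1754 enrolled. Section 1.4.1: 8 endpoint 1 event subjects among 279, of whom 2 exited before the 6-month visit.

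**The plan's figures reproduce.**

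- n = [(1.960·√(0.925·0.075) + 0.842·√(0.9475·0.0525)) / 0.0225]² = 978.85, i.e. 979.
- 979 / 0.89⁵ = 979 / 0.5584 = 1753.2, i.e. 1754.
- Exact test at n = 979: pass with at least 922 complication-free (at most 57 failures). Alpha is 0.0236 and power at 94.75% is 0.811.

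**Effect of the completers rule.** Let S be the true 5-year complication-free rate and f the share of complication subjects who leave because of the complication, beyond ordinary attrition. The documents do not give f. The expected rate among completers is

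q = S / [S + (1 − S)(1 − f)].

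At S = 0.925 and f = 0.25, q = 0.925 / (0.925 + 0.05625) = 0.9427. The chance of passing is the binomial probability of reaching the critical value. It is shown with n fixed at 979, and with n reduced to 1754 × 0.5584 × [S + (1 − S)(1 − f)] and the critical value recomputed.

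| f (true rate 92.5%) | Expected rate | Pass, n = 979 | Pass, reduced n |
|---|---|---|---|
| 0 | 92.5% | 2.4% | 2.4% |
| 5% | 92.8% | 5.7% | 4.6% |
| 10% | 93.2% | 12% | 11% |
| 20% | 93.9% | 39% | 39% |
| 25% | 94.3% | 58% | 53% |
| 30% | 94.6% | 76% | 73% |

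Simulating 1754 subjects with random dropout at f = 25% gave about 54% to 56%. If the true rate is 91.0%, below the goal, the reduced-n chance of passing is 9% at f = 25% and 94% at f = 50%.

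**A concrete case.** With 73 failures in 979 (906/979 = 92.5%), the lower bound is 90.7% and the test fails. If 17 of the 73 leave because of their complication, 56 failures in 962 remain (906/962 = 94.2%), the lower bound is 92.507% and the test passes.

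**The pathway in the trial's own data.** Section 1.4.1 reports n = 2 who "experienced an endpoint related adverse event but exited the study prior to reaching the 6 month follow-up". A completers-only rule would have given 271/277 = 97.8% instead of the reported 271/279 = 97.1%.

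**Copying the endpoint 1 rule would over-correct.** That rule keeps all observed events but drops event-free exits. Take constant hazards h = −ln(0.9475)/5 and λ = −ln(0.89).

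- Observed events: h/(h+λ) × [1 − e^(−5(h+λ))] = 0.0399.
- Event-free completers: 0.9475 × 0.5584 = 0.5291.
- Estimate: 0.5291 / (0.5291 + 0.0399) = 93.0%, against a truth of 94.75%.

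In simulation, power was then about 7%. With events concentrated early, the mean was about 92% and power lower still.

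**Kaplan-Meier alternative.** Across simulations of 1754 subjects with 11% yearly independent dropout and constant or early-weighted hazards, the log-log lower bound passed about 2% to 3% of the time at a true 92.5%. It passed 90% to 94% of the time at 94.75%. Under a constant hazard at 94.75%, its Greenwood standard error is 0.0062, against √(0.9475·0.0525/979) = 0.0071 for the completer binomial.

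**The case against.** The strongest reply is that the text conflicts with itself and does not consistently delete failures. Section 2.3.4 begins with all implanted subjects, Section 6.6.2 includes all qualifying events and lead-related deaths, and Section 3.5.2.3 says data collected up to withdrawal of consent will be used. Section 5.1 gives the Clinical Events Committee the final decision on which events enter endpoint 3. The conflict is real, but the sentence that fixes who is analysed is explicit, and the committee's authority covers events, not subjects. None of these passages supplies a rule for keeping early exits with an event.

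The size is also open to challenge, and this largely stands. Two of 8 has an exact 95% interval of 3% to 65%, and no exit reasons are given. Half of those 8 events were dislodgements, which endpoint 3 excludes within 45 days. Subjects who are repositioned or given another Sentus QP lead stay in the study. The figures are therefore a range over f, not a prediction.

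There is mitigation. Section 2.3.7 requires a report to FDA if the Kaplan-Meier rate falls, or is projected to fall, below 92.5%. Section 2.5.4 allows additional missing-data analyses, and endpoints 7 and 8 carry no hypothesis test. This makes it less likely that a poor result goes unseen, but it does not repair the primary test.

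The conflict with Section 3.5.2.2 is weaker than the others, because that section does not name endpoint 3 and Section 2.2.3 starts observation after successful implantation. Section 2.2.1 has the same start for endpoint 1, however, and there lead-caused implant failures were still included.

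**Conclusion.** The concern holds. As written, endpoint 3 and secondary endpoints 7 and 8 exclude subjects whose complication ended their participation, contrary to the failure definition in Section 6.6.2. The bias favours the lead. At a true rate of 92.5%, the chance of passing rises from 2.4% to 11–12% if a tenth of complication subjects leave because of the event, and to 53–58% if a quarter do. Even 5% roughly doubles it.

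These sizes rest on an assumed f, a common f across event types, and ordinary attrition unrelated to complications. The direction needs only that some complications cause exit, which Section 3.5.2.5 guarantees for explants without a new Sentus QP lead. Because this is the primary safety test, it must be corrected before 60-month data are analysed.

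**What to change.** Reconcile Sections 2.3.4, 2.3.5, 3.5.2.2, 3.5.2.5 and 6.6.2, and rewrite the analysis as follows:

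1. Test endpoint 3 with the Kaplan-Meier 5-year complication-free estimate in all U.S. subjects with a successful implant. Success requires the lower two-sided 95% bound (Greenwood variance, log-log scale) to exceed 92.5%.
2. Count every adjudicated Table 8 event, other Section 6.6.2 event and lead-related death on its date. State that an event on the termination date is an event and not a censoring, since Section 3.5.3 puts explant and exit on the same day. Censor event-free exits as Section 2.5.4 already does.
3. Say whether implant failures caused by a lead complication enter as events at day 0, as they did for endpoint 1, and align the observation period in Section 2.2.3. Including them is preferable.
4. Use the same analysis set for secondary endpoints 7 and 8.
5. Keep the completer binomial as a sensitivity analysis. Because unrelated deaths are censored, add a cumulative-incidence analysis treating them as a competing event.
6. Do not carry over the endpoint 1 rule.

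The cost is a protocol and SAP amendment that changes the test basis in Section 2.4.2, with the sample-size justification restated. The simulated power of 90% to 94% with 1754 subjects suggests that enrolment need not grow. The curve and censoring rule are already planned, and no new data are needed. The reported rate may be somewhat less favourable.

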2.3.5 Secondary Endpoints

The secondary endpoints of pacing threshold (programmed and novel pacing vectors), sensed amplitude, and impedance at the 3 month visit will be summarized using standard measures, including means, standard deviations, medians, minimum and maximums. In addition, the percentage of subjects with values within the acceptable range per lead model will be provided. Acceptable ranges for the lead measurements are provided in Section 3.2.5.

For secondary endpoints 1-4 only subjects who were successfully implanted, completed a 3 month visit, and have data for the specific endpoint being evaluated will be included in the endpoint analysis; however, additional data resources may be used for supplemental analysis.

For the endpoint 5, time-to-first-complication, the analysis set of the primary endpoint 1 and additionally also those subjects who drop out prior to the 6-month follow-up is used. Confidence intervals based on Kaplan-Meier estimates for freedom from complications together with the associated standard errors will be provided. For this estimate, subjects exiting the clinical investigation prior to the 6 month visit will be censored at the time of study termination.

For endpoint 7 and 8, only subjects who were successfully implanted and completed a 60-month month visit will be included in the endpoint analysis; however, additional data resources may be used for supplemental analysis.

2.3.6 Additional Data of Interest Analysis

For additional data of interest, descriptive summary statistics appropriate to the type of parameter, continuous or discrete, will be reported.

Pacing threshold, R-wave sensing and impedance measurements for the Sentus QP leads at pre-hospital discharge/wound check, 3, 6, and 12 months, plus additional required follow-up visits (i.e., 18 months, 24 months) will be summarized using standard measures, including means, standard deviations, medians, minimums, and maximums. Data will be provided as a total at each visit interval and per lead model at each visit interval.

2.3.7 Trend Analyses

The primary post-approval safety endpoint is evaluated at 5 years post-implant against a prespecified performance level (92.5% for overall freedom from Sentus QP related complications). To monitor the ongoing incidence of any potential AEs against the accumulating follow-up exposure post-implant, a Kaplan-Meier survival curve will be prepared at the reporting intervals for this safety outcome. Root causes for any failures, regardless of the incidence rates, will be investigated.

If the observed cumulative survival rate falls below the 5-year target value (92.5% of overall freedom from complications) at any time during the study, or is projected to fall below the target value, then BIOTRONIK will summarize the observed data and the results of the failure investigations, and report the findings to the FDA at or before the next scheduled reporting interval. If at any time a single unanticipated adverse event or device failure, or combination of events, is believed to have implications regarding the safety of current or future subjects, then this will be reported to the FDA within the statutory timeframes.

2.4 Estimated Sample Size

2.4.1 Pre-Market Analyses

The sample size required to evaluate primary hypotheses 1 and 2 was estimated using the following design criteria:

- Study design: non-randomized
- Test basis: exact binomial test
- Type I error, alpha: 2.5% (one-sided)
- Statistical power: 80% for acceptance of both primary Alternative hypotheses

For primary safety hypothesis (complication-free rate), the following assumptions apply:

- Expected complication-free rate through 6 months: 95.0%
- H_A: Complication-free rate through 6 months post-implant > 90.0%

For primary efficacy hypothesis (LV pacing threshold for permanently programmed vector), the following assumptions apply:

- Expected rate of acceptable LV pacing thresholds at 3 months: 93.0%
- H_A: Acceptable LV pacing threshold rate at 3 months > 88.0%

Based on the above criteria, a total of 231 evaluable subjects assessed at 6 months would be required to accept the primary safety alternative hypothesis (endpoint 1). For primary endpoint 2, a total of 282 evaluable subjects assessed at 3 months would be required to accept the primary efficacy alternative hypothesis.

An adjustment of 10% is used in the sample size estimation for both primary endpoints 1 and 2 to account for subjects that exit the clinical investigation prior to having a 6 month evaluation. Reasons that subjects may exit the clinical investigation include withdrawal of consent, mortality, device explant, change in physician, or subject moving. Therefore, up to 314 subjects (=282/.9) will need to be enrolled to account for premature study terminations.

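### Section 2.4.1 words its 80% power as joint power for both pre-market hypotheses, but 231 and 282 give about 80% for each separately; joint power is about 66% to 72% if the endpoints are independent

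*Combined protocol and SAP*

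**What the plan says.** Section 2.4.1 of the combined protocol and SAP lists one set of design criteria for primary hypotheses 1 and 2: a non-randomised design, "Test basis: exact binomial test", a one-sided type I error of 2.5%, and "Statistical power: 80% for acceptance of both primary Alternative hypotheses".

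It then gives assumptions for each endpoint. For endpoint 1, the expected complication-free rate through 6 months is 95.0% against a goal of 90.0%. For endpoint 2, the expected rate of acceptable LV pacing thresholds at 3 months is 93.0% against a goal of 88.0%.

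From these criteria the section concludes that "a total of 231 evaluable subjects assessed at 6 months would be required" for endpoint 1, and that 282 evaluable at 3 months are needed for endpoint 2. Enrolment of up to 314 is 282 divided by 0.9. Section 2.3.1 ties the pre-market cohort to the same two counts. No section gives a joint power calculation, a correlation between the endpoints, or a split of the power between them.

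**The concern.** Power to accept both alternatives normally means the probability of one event: success on endpoint 1 and on endpoint 2 in the same study. Two tests with about 80% power each do not have 80% power for that event unless their outcomes are almost completely dependent.

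Section 2.4.2 sizes the study for the single hypothesis 3 and states its 80% power without any such qualifier. The extra words in 2.4.1 therefore read as a deliberate joint target. A reader who takes them at face value would credit the pre-market design with an 80% chance of meeting both endpoints. What is at stake is whether the protocol describes its own design accurately.

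**Working it through.** **Inputs** (all from Section 2.4.1): exact binomial test; one-sided alpha 0.025; endpoint 1 at p0 = 0.90, p1 = 0.95, n = 231; endpoint 2 at p0 = 0.88, p1 = 0.93, n = 282. The correlation between the endpoints is not given, so independence is the base case and the full feasible range is shown.

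**Step 1: reproduce the plan's sizes.** For each n, the critical count r is the smallest value with P(X ≥ r | n, p0) ≤ 0.025. Power is P(X ≥ r | n, p1).

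| Endpoint | n | r | Exact alpha | Power |
|---|---|---|---|---|
| 1 | 230 | 217 | 0.0134 | 73.7% |
| 1 | 231 | 217 | 0.0239 | 81.6% |
| 2 | 281 | 259 | 0.0157 | 75.2% |
| 2 | 282 | 259 | 0.0246 | 81.2% |

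A search over n confirms that 231 and 282 are the smallest sizes with at least 80% power for each endpoint alone. The normal approximation would have given 239 and 291. The plan's sizes are therefore per-endpoint sizes from the exact test.

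**Step 2: joint power under independence.**

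- At 231 and 282: 0.8164 × 0.8122 = 0.663.
- With 282 evaluable for both, endpoint 1 needs at least 264 successes (exact alpha 0.0221) and has power 88.3%. Joint power is 0.8827 × 0.8122 = 0.717.

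Exact power does not rise smoothly with n, so sizes between these two need not give values between 66% and 72%. At 240 for endpoint 1 the product is 63.1%; at 279 it is 0.8363 × 0.8122 = 67.9%.

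**Step 3: allow for correlation.** The same subjects contribute to both endpoints. Let q be the probability that a subject fails both. With failure rates of 0.05 and 0.07, q can run from 0 to 0.05, and

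phi = (q − 0.05 × 0.07) / √(0.05 × 0.95 × 0.07 × 0.93).

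The endpoint 1 subjects were taken as a subset of the endpoint 2 subjects, with 2 million simulated trials per row.

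| q | phi | Joint power, 231 and 282 | Joint power, 282 for both |
|---|---|---|---|
| 0 | −0.06 | 65.9% | 71.3% |
| 0.0035 | 0 | 66.3% | 71.7% |
| 0.01 | 0.12 | 67.1% | 72.4% |
| 0.02 | 0.30 | 68.6% | 73.6% |
| 0.03 | 0.48 | 70.1% | 75.0% |
| 0.05 | 0.84 | 74.1% | 79.0% |

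Joint power is below 80% in every row, including the last, where every endpoint 1 failure is also an endpoint 2 failure.

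**Step 4: what a joint 80% would have needed.** Under independence with equal power per endpoint, each needs √0.80 = 89.4%. The smallest exact sizes are 292 and 361, and 361/0.9 = 401.1, or 402 enrolled. Alternatively, a single common evaluable size of 331 first reaches 80% joint power, and 331/0.9 = 367.8, or 368 enrolled.

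**The case against.** The strongest reply is that *both* was meant as *each*. Section 2.4.1 lists shared criteria first, then separate assumptions and a separate size per hypothesis. In that layout the power line can be read as applying 80% to each of the two hypotheses. The sizes fit that reading exactly, and nothing in the plan was derived from a joint target. This probably describes what was intended. It explains the sentence but does not make it correct as written: the literal wording describes joint acceptance.

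A second reply is that 231 is only the minimum for endpoint 1. Enrolment is driven by endpoint 2, so endpoint 1 should have more than 231 evaluable; Section 1.4.1 reports 279. This stands, and it is why 66% should not be quoted alone.

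A third reply is that general probability limits leave room for 80%. From the two marginal powers alone, joint power could lie anywhere from 0.8164 + 0.8122 − 1 = 62.9% to 81.2%. Those limits ignore how the data arise. Once the same subjects supply both endpoints at the planned failure rates, the attainable ranges are those in Step 3 and exclude 80%.

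Finally, the point changes no remaining decision. Sections 1.4 to 1.4.2 report the pre-market analysis as done and both endpoints as met: 271/279 (p < 0.0001) and 267/286 (p = 0.002). That is right, and it limits the weight of the point.

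**Conclusion.** The sentence is wrong as written, and the correction is minor. The stated sizes deliver 81.6% and 81.2% power separately. Joint power is about 66% at 231 and 282, and about 72% with 282 for both, assuming independence. Over all feasible correlations the ranges are about 66% to 74% and 71% to 79%. These figures rest on the plan's own expected rates and on shared subjects. If *each* was intended, the sizes are correct and only the wording is at fault.

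Two stronger readings are not supported. A reader might infer that the pre-market study was too small or that its conclusions are in doubt. The sizes are right for the per-endpoint target, both endpoints were met, and planned power has no bearing on the type I error of the completed tests. A reader might also infer that the plan formally required success on both endpoints. Section 2.5.1 defines pre-approval success only by reference to FDA's approval requirements and states no such rule. The relevance of joint power therefore comes from the wording of 2.4.1 and from the plan having two pre-market primary endpoints. Endpoint 3 has its own power statement in Section 2.4.2 and is not affected.

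**What to change.** Replace the power line in Section 2.4.1 with wording such as: *80% power for each primary hypothesis separately; joint power for both is about 66% with 231 and 282 evaluable subjects and about 72% with 282 evaluable for both, assuming independent endpoints.*

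The cost is one sentence, and the stated design property becomes less favourable. Enrolment, type I error and the reported pre-market results stay as they are. Resizing to the figures in Step 4 would serve no purpose now that the pre-market analysis is complete.
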